***exceptions to this are carcinoma in situ or fully resected basal and squamous cell cancer of the skin.**

4.4 Exclusion Criteria

To participate, a subject **MUST NOT HAVE**:

1. A life expectancy <12 months
2. A CT scan or baseline cardiac MRI showing new tumor or suspicious lymphadenopathy raising concern of malignancy
3. Presence of obstructive CAD as determined via imaging within 5 years prior to study enrollment provided there have been no symptoms or evidence of CAD since the test (see section 4.1 for imaging guidance)
4. Had a previous myocardial infarction
5. A history of radiation therapy AND evidence of constrictive physiology and/or evidence of other patterns of non-ischemic cardiomyopathy on cardiac MRI (e.g., amyloidosis, sarcoidosis, hemochromatosis, pure radiation-induced cardiomyopathy, etc.) not consistent with AIC being the dominant etiology of heart failure
6. Valvular heart disease including 1) mechanical or bioprosthetic heart valve; or 2) severe valvular (any valve) insufficiency/regurgitation within 12 months of consent
7. Aortic stenosis with valve area $\leq 1.5\text{cm}^2$
8. A history of LV reduction surgery or cardiomyoplasty
9. Evidence of cardiogenic shock
10. A history of ischemic or hemorrhagic stroke within 90 days of baseline testing
11. Liver dysfunction during baseline testing, as evidenced by enzymes (e.g., AST, ALT, alkaline phosphatase) greater than 3 times upper limit of normal
12. Diabetes with poorly controlled blood glucose levels (HbA1c $> 8.5\%$)
13. An underlying autoimmune disorder or current immunosuppressive therapy (e.g., chronic corticosteroid, rheumatologic or immune modulating therapy) or likelihood of use of immunosuppressive therapy during participation in the trial (*medications will be considered on a case by case basis*)
14. A baseline eGFR $<35 \text{ ml/min}/1.73\text{m}^2$
15. A contrast allergy that cannot adequately be managed by premedication
16. Received gene or cell-based therapy from any source within the previous 12 months

15. A contrast allergy that cannot adequately be managed by premedication

16. Received gene or cell-based therapy from any source within the last 12 months

CONFIDENTIAL AND PROPRIETARY

17. A hematologic abnormality during baseline testing as evidenced by hemoglobin < 9 g/dl; hematocrit < 30%; absolute neutrophil count < 2,000 or total WBC count more than 2 times upper limit of normal; or platelet values < 100,000/uL
18. Evidence of active systemic infection at time of study product delivery
19. HIV, and/or active HBV or HCV
20. Coagulopathy (INR > 1.5) not due to a reversible cause (e.g., warfarin and/or Factor Xa inhibitors) (see Section 6.4 re: injection procedure and anticoagulation therapy) *Note: Subjects who cannot be withdrawn from anticoagulation will be excluded.*
21. Presence of LV thrombus (*See guidance in Section 6.6.3*)
22. Presence of a pacemaker and/or ICD generator with any of the following limitations/conditions:
 - manufactured before the year 2000
 - leads implanted < 6 weeks prior to consent
 - non-transvenous epicardial or abandoned leads
 - subcutaneous ICDs
 - leadless pacemakers
 - any other condition that, in the judgment of device-trained staff, would deem an MRI contraindicated
23. Pacemaker-dependence with an ICD (*Note: pacemaker-dependent candidates without an ICD are not excluded*)
24. A cardiac resynchronization therapy (CRT) device implanted less than 3 months prior to consent
25. Other MRI contraindications (e.g. patient body habitus incompatible with MRI)
26. An appropriate ICD firing or anti-tachycardia pacing (ATP) for ventricular fibrillation or ventricular tachycardia within 30 days of consent
27. Ventricular tachycardia \geq 20 consecutive beats without an ICD within 3 months of consent, or symptomatic Mobitz II or higher degree atrioventricular block without a functioning pacemaker within 3 months of consent
28. A history of drug abuse (use of illegal "street" drugs except marijuana, or prescription medications not being used appropriately for a pre-existing medical condition) or alcohol abuse (\geq 5 drinks/day for > 3 months), or documented medical, occupational, or legal problems arising from the use of alcohol or drugs within the past 24 months
29. Cognitive or language barriers that prohibit obtaining informed consent or any study elements (interpreter permitted)
30. Participation (currently or within the previous 30 days) in a cardiac related investigational therapeutic (including stem cell based therapies) or device trial
31. Pregnancy, lactation, plans to become pregnant in the next 12 months, or is unwilling to use acceptable forms of birth control during study participation
32. Any other condition that, in the judgment of the Investigator or Sponsor, would be a contraindication to enrollment, study product administration, or follow-up

4.5 Baseline Testing Window

The baseline testing period extends from the date the ICF is signed until the study product injection (SPI) procedure. This period will not exceed 45 days. Should subjects fail baseline testing for a reason that is likely to change over time, they may be considered for re-testing. See section 6.2 for procedures and assessments to be performed during the baseline testing period.

CONFIDENTIAL AND PROPRIETARY

Individuals meeting enrollment criteria will be scheduled to undergo the SPI procedure (see section 5.4) and randomized to cells or placebo (see section 4.6). The SPI procedure will occur no less than three days after randomization and no more than 45 days from signing the ICF.

4.6 Randomization Procedures and Timing

Randomization to treatment assignment (cells or placebo) will be conducted using a web access database created and maintained by the Data Coordinating Center (DCC). The research coordinator (RC) will randomize the subject via the CCTRN web-based database which will perform the computer-generated randomization assignment and send automatic emails notifying the study team that the treatment assignment can be accessed by unblinded study team members with appropriate security credentials. The RC will not randomize the subject until the following criteria are met: i) the subject has provided written informed consent, ii) baseline evaluations are complete, iii) the inclusion and exclusion criteria for the study have been satisfied, and iv) MSC product is available at the cell manufacturing facility (CMF) should the subject be randomized to the cell group. Randomization should occur no less than 3 days prior to the scheduled SPI procedure (to allow time for cell shipping and local product preparation) and no more than 7 days prior to the scheduled SPI procedure (to minimize the risk of randomizing subjects who do not receive treatment).

5.0 STUDY PRODUCTS AND DELIVERY

The study products (allo-MSCs and placebo) are each individually described but shall be referred to throughout the protocol as “study product”.

5.1 Allogeneic Mesenchymal Stem Cells (allo-MSCs)

The MSC cell bank will be prepared at the Center for Cell and Gene Therapy (CAGT) GMP Facility at Baylor College of Medicine which will be referred to as the Central Cell Manufacturing Facility (CCMF). The CCMF has a Facility Masterfile at the FDA describing its infrastructure and operations. In brief, the facility consists of 22 ISO 7 clean rooms in which manufacturing is performed. The MSC will be manufactured using the Terumo Quantum Cell Expansion system. This is a functionally-closed computer-controlled bioreactor. The cells adhere to hollow fibers that are pre-coated with recombinant Fibronectin. The cells are fed by continuous flow of medium through the bioreactor. After 48 hours the non-adherent cells are flushed from the bioreactor and feeding continues. Cell growth is assessed by measurement of glucose consumption and lactate production. When lactate levels reach 4mM/liter the flow of medium is doubled to 0.2 ml/min. This process is repeated until the flow rate has reached 0.4ml/min and the lactate levels are above 4mM. At this point the bioreactor is flushed with 2.5 times the reactor volume of phosphate- buffered saline. 180ml of recombinant trypsin (TrypLE Select) is added to the reactor for 15min to detach the cells. These are then automatically harvested into a bag containing growth medium.

For passage two the cells are seeded into the Fibronectin coated bioreactor cartridge at $\sim 1 \times 10^4$ cells/ cm^2 . Growth kinetics are monitored as described above. Harvesting is performed when the flow rate reaches 1.6ml/min and the lactate concentration reaches 4mM/liter.

All operations are programmed into the bioreactor and reagent transfers are performed using sterile connect devices or aseptic connectors. Samples are taken for testing aseptically within an ISO 5 biological safety cabinet. This procedure has been reviewed by the Food and Drug Administration and approved for use in a separate IND submission.

CONFIDENTIAL AND PROPRIETARY

For subjects randomized to receive allo-MSCs, allogeneic bone marrow donor-derived MSCs will be provided (Appendix A), according to established protocols, by the CCMF. The availability of allo-MSCs offers the potential for an “off the shelf” product for patients. Significant data have been generated (see section 2.4) to demonstrate that allo-MSCs are immunosuppressive⁷³⁻⁷⁵. In addition, allo-MSCs are immune-privileged and can be infused without immune rejection despite disparate HLA phenotypes⁵⁶.

5.1.1 Shipment of Cryopreserved allo-MSC Allografts

The cells will be cryopreserved at the CCMF according to their standard operating procedures (SOPs) using a controlled-rate freezer and stored in the vapor-phase of liquid nitrogen in continuously monitored cell storage banks. Twenty-four hours prior to shipment, a validated liquid nitrogen dry shipper will be charged with liquid nitrogen. The following morning any remaining non-absorbed liquid nitrogen will be decanted from the dry shipper and the vials containing the frozen MSC will be transferred to the shipper. The Data Logger (temperature monitor) located in the lid will be activated and the shipper sent via Federal Express to the local cell processing laboratories (CPLs) following CCMF SOPs within one week prior to the scheduled injection procedure. The CCMF will also provide all relevant SOPs for product preparation for administration. Certificates of Analysis (COA) will be provided by the CCMF with each product shipped to the local CPL.

5.1.2 Preparation for Administration of-MSC Allografts

Relevant SOPs and worksheets used for thawing, washing, and testing of allo-MSC product will be provided by the CCMF. The allo-MSC product will undergo QC testing before injection as indicated in Table 2a.

1X10⁸ allo-MSCs will be provided in a final volume of 8.0 ml of Buminate solution 5% HSA, at a cell concentration of approximately 12.5X10⁶ total cells / ml. The physician will administer 20 individual doses of 5X10⁶ cells/0.4ml, per dose, per injection site. The 20th injection will be followed by 0.1 ml of saline to flush any residual cells from the line into the 20th injection site. It is permissible to prepare more than 8.0 ml of cell suspension, at a maximum concentration of 12.5X10⁶ cells / ml. However, any excess volume remaining after delivery of the 20 injections shall not be injected and shall be discarded according to institutional guidelines.

Table 2a. Testing of allo-MSCs for Injection

Assay	Test Method	Specification
Viability*	Trypan blue	≥70
Cell Count*	Manual	1x10 ⁸
Rapid Sterility*	Gram Stain	No organisms
Endotoxin*	EndoSafe PTS	< 5EU/kg**
Aerobic, Anaerobic, and Fungal	14 day Bactec/BacT/ALERT assay or equivalent	No Growth

* Tests done for release criteria specification prior to injection

** Based on recipient weight and product volume

5.2 Placebo Group

Subjects randomized to the placebo group will undergo the same baseline testing and imaging as those in the allo-MSC group. The placebo will be kept on site at the local CPLs. The fifteen

CONFIDENTIAL AND PROPRIETARY

patients in the placebo group will receive transendocardial injections of cell-free Buminate solution in 20 injection sites. The placebo product will undergo QC testing before injection as indicated in Table 2b.

Table 2b. Testing of Placebo for Injection

Assay	Test Method	Specification
Rapid Sterility*	Gram Stain	No organisms
Endotoxin*	EndoSafe PTS	< 5EU/kg**
Aerobic, Anaerobic, and Fungal	14 day Bactec/BacT/ALERT assay or equivalent	No Growth

* Tests done for release criteria specification prior to injection

** Based on recipient weight and product volume

5.3 Blinding of the Interventionalist and Study Team

With regard to safety, the interventionalist must be able to visualize the study product to inspect that it looks safe (e.g., free of air bubbles, clumping, etc.). As the study product cannot be effectively masked, the process of blinding resides with endpoint and adverse event determination. The cMRI endpoint will be determined by core laboratories. Core laboratory evaluation of endpoint measures will be conducted by personnel who are blinded to therapy assignment. Coordinators and other personnel participating in the collection of cMRI, 6MWT, and the MLHFQ endpoint data will also be blinded to the therapy assignment. In addition, each of the clinical centers will take steps to ensure that adverse event assessments are carried out in a blinded fashion.

Local CPL and CCMF staff will be unblinded (see section 4.6) in order to assist with product preparation; however, the research teams (investigators, coordinators and other staff involved with endpoint data collection and event data) will be blinded to the treatment assignment. If for important medical reasons unblinding is thought to be necessary, the Investigator may identify the treatment assignment by contacting the DCC who is responsible for maintaining randomization records for all subjects.

5.4 NOGA Catheterization Procedure

Intramyocardial cell delivery by NOGA will be used in this trial. All investigators performing the catheter-based study procedures will receive appropriate training in the use of the catheters by the catheter manufacturer (Biologic Delivery Systems). All interventionalists will be certified under this training program. Site interventional cardiologists will meet routinely by teleconference to review injection procedures to assure that they are standardized across sites.

Left ventricular (LV) cine angiography will be performed in orthogonal planes (typically RAO 30 and LAO 60 degree projections). End-diastolic endocardial contours will be saved as angiographic image recordings in both projections, to provide guidance regarding location of LV borders during fluoroscopic manipulation of the injection catheter.

LV electromechanical mapping (EMM) will be performed using NogaStar catheter(s), sized appropriately for the LV dimension. An 8 French femoral artery sheath of sufficient length will be chosen to aid operators in negotiating pelvic vasculature with the NOGA catheter.

Unfractionated heparin will be used to maintain an activated clotting time (ACT) between 200 and 250 seconds during NOGA mapping and injection. The mapping catheter is retrogradely

IRB NUMBER: HSC-SPH-15-0443

CONFIDENTIAL AND PROPRIETARY

advanced across the aortic valve into the LV cavity. EMM will be performed according to standard clinical practice, with attention to achieving a smooth endocardial contour and accurate representations of the long and short axes of the LV chamber.

For the cell or cell-free transendocardial study product injection (SPI) procedure, the MyoStar NOGA injection catheter will be prepared by adjusting the needle extension at 0° and 90° flex and priming the catheter by injecting the study product until a drop is observed at the extended needle tip (approximately 0.1 cc). All study product will be retained to complete the 20 required injections. To ensure safety and limit potential for extracardiac administration of the injectate, the needle extension will be adjusted to ensure that the needle length is ≤ 0.5 mm and will not exceed 50% of target tissue thickness when assessed at both 0° and 90°. The injection catheter will be advanced to the aortic valve, and placed into the LV in retrograde fashion.

Priority for selecting the 20 injection sites will be based upon the objective of delivering the study product in a minimum of four myocardial segments according to the AHA 17 segment polar map) selected by the investigator to be a territory which is: a) safely treatable with low risk of perforation or other complications; b) avoiding the true LV apex and other areas known to be < 6 mm in myocardial thickness, and avoiding the left bundle branch site of earliest activation; c) clinically important based on viability assessments provided below; and, d) accessible with the tip of the selected MyoStar catheter.

The NOGA map obtained will be unique in that it will display heterogeneous distribution of unipolar voltage in the LV, typical of patients with dilated cardiomyopathy. This is thought to represent areas of relative fibrosis and will serve as the basis for selection of the target injection area. The operator will proceed to delineate an injection area using the criteria mentioned above and ideally select injection sites that demonstrate intermediate level unipolar voltage (4 to 8mV). This range can be expanded to include areas with unipolar voltage of up to 12mV if necessary.

Sites for injection should satisfy the following criteria: (1) perpendicular position of the catheter to the LV wall; and (2) loop stability < 4mm. Ideally the majority of injections will be placed at a site with a voltage threshold of ≥ 4mV and ≤ 8mV. *When selecting sites for injection generally those with a voltage < 4mV will be avoided unless there are no higher unipolar voltage values present on the unipolar voltage map.*

Each of the 20 injections will contain either 0.4 ml of cell suspension with 5 million allo-MSCs per injection site for the active cell treatment arm or 0.4 ml of cell-free Buminate solution for the placebo group. For the final injection, 0.1 cc of saline should be placed in the catheter and injected. This will allow the 0.1 cc already in the catheter (from priming) to be administered into the myocardium, constituting the 20th injection. Each injection should be infused over 60 seconds.

Sites of injection will be marked and recorded by a solid circular tag on the NOGA map accompanied by a reference to injection number and presence or absence of needle-induced extrasystole. Sites of injection may also be recorded on cine fluoroscopy, and demarcated as a dot with the corresponding injection series number on overlay tracings in both RAO and LAO projections.

After the injection procedure, subjects will be monitored overnight. A 2-D echocardiogram will be performed post SPI (within 6 hours). Additional echocardiographic assessments for pericardial effusion will be done only as clinically indicated. Troponin I or T will be collected 8 (+/- 2) hours post-injection catheter procedure and again prior to discharge. An analysis of the impact of biomarker elevations on measures of LV function and MACE will be carried out. We believe this will demonstrate that biomarker elevations are not related to study outcomes.

CONFIDENTIAL AND PROPRIETARY

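### The operator sees the unmasked product and also chooses the injection sites, and the protocol does not require the site plan to be fixed first, so site selection could differ by arm

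*Combined protocol and SAP*

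**What the plan says.** Section 5.3 (Blinding of the Interventionalist and Study Team) states that "the interventionalist must be able to visualize the study product to inspect that it looks safe". It draws the consequence openly: "As the study product cannot be effectively masked, the process of blinding resides with endpoint and adverse event determination". The same section also says that "the research teams (investigators, coordinators and other staff involved with endpoint data collection and event data) will be blinded to the treatment assignment".

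Section 5.4 (NOGA Catheterization Procedure) makes investigators the operators: "All investigators performing the catheter-based study procedures will receive appropriate training in the use of the catheters". It describes electromechanical mapping, then preparation of the injection catheter, which includes "priming the catheter by injecting the study product until a drop is observed at the extended needle tip", and then the choice of sites. The 20 injections go to at least four of the 17 AHA segments, "selected by the investigator to be a territory which is" safe to treat, clinically important and reachable. On voltage, "The operator will proceed to delineate an injection area using the criteria mentioned above and ideally select injection sites" between 4 and 8 mV. The section adds: "This range can be expanded to include areas with unipolar voltage of up to 12mV if necessary". Sites below 4 mV are generally avoided unless the map shows nothing higher. Each injected site is tagged and numbered on the map.

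The feasibility measures (Sections 3.4.2 and 8.3.2.2) report subjects with fewer than 20 injections and subjects who did not receive the intended cell dose. They do not cover segment, voltage or location.

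**The concern.** The person who can tell cells from placebo by sight decides where the product goes. If the decision is made, or can be revised, after the product is visible, knowledge of the arm could influence how widely the injections are spread and which voltages are accepted. That is performance bias. Core-laboratory reading and blinded event assessment protect against biased measurement, but they would faithfully record any real difference that arose in the catheterization laboratory.

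Three planned comparisons depend on comparable delivery: procedure-related safety items such as tamponade and ventricular tachycardia or fibrillation (Sections 3.4.1 and 8.3.2.1), completion of all 20 injections (Section 8.3.2.2), and the cMRI changes (Section 8.3.2.3). Section 5.4 itself links the choice of territory to perforation risk. If the choice varied with arm, the cell versus placebo contrast would mix the effect of the product with the effect of where it was put.

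**Working it through.** The plan states no figure on this point, so the check is mainly a reading of the sections against each other.

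**1. Is the person who sees the product the person who picks the sites?** Section 5.3 says the interventionalist inspects the product. Section 5.4 says investigators perform the catheter procedures and that all interventionalists are certified, and it assigns the choice of territory to the investigator and of sites to the operator. No other person, blinded or not, is given that task.

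**2. What is fixed and what is open?**

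| Element | Rule | Same in both arms? |
|---|---|---|
| Number, volume | 20 × 0.4 ml = 8.0 ml | Fixed |
| Cell dose (active arm) | 20 × 5 million = 100 million; 8.0 ml × 12.5 million/ml = 100 million | Fixed, internally consistent |
| Infusion time | 60 seconds per injection | Fixed |
| Anatomy | No true apex, no wall under 6 mm, not the earliest-activated left bundle site | Firm |
| Catheter | Perpendicular, loop stability under 4 mm | Firm |
| Segment spread | At least 4 of 17 (4/17 = 24%) | Operator's choice above the minimum |
| Voltage | Preferred 4–8 mV (4 mV wide), extendable to 12 mV (8 mV wide); no trigger stated, and no number given for the preferred majority | Operator's choice |

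The discretion is confined to location.

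**3. Is the plan fixed before the product is seen?** Sections 5.3 to 5.5 contain no such requirement. Manuals of operations are cited for the walk test and the cMRI, but not for site selection. Tagging on the map records injected sites, not intended ones.

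**4. Would a check after the trial be enough?** The documents give no SD for any delivery measure, so differences are in SD units. Inputs are 15 per arm (Executive Summary) and two-sided 0.05 (Section 8.6).

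- Standard error of a difference: √(2/15) = 0.365 SD.
- 95% CI half-width: t(0.975, 28 df) × 0.365 = 2.048 × 0.365 = 0.75 SD.
- Power (normal approximation) = Φ(d/0.365 − 1.96): 13% at d = 0.3, 28% at 0.5, 59% at 0.8.
- Difference needed for 80% power: (1.96 + 0.84) × 0.365 = 1.02 SD.

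A moderate imbalance in segments or voltage would probably go undetected. Fixing the plan beforehand does work that a later comparison cannot.

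**5. Related inconsistencies.** Section 3.3 says the 20 injections treat the whole left ventricle and refers to Section 5.4, which sets a minimum of four segments. Section 5.3 says investigators are blinded, while Section 5.4 has investigators perform a procedure in which they see the product. The qualifier about staff involved in data collection may be meant to exclude operators, but the text does not say so.

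**The case against.** The strongest reply is that the protocol acknowledges the unmasked operator and contains the consequences. The firm limits in the table apply to every patient. Safe sites are required in both arms, so choosing them is the rule and not a sign of knowing the arm. Some discretion is unavoidable because maps, wall thickness and access differ between patients. Operators are certified and meet by teleconference, injected sites are recorded, assessment is blinded, and Section 8.6 calls the findings preliminary. All of this stands and limits the point. It does not close the gap: the teleconferences standardise across sites and not between arms, and no by-arm comparison of the recorded sites is planned.

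A reader might infer three stronger things that the documents do not support.

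- *That sites are chosen after the product is seen, because priming is described first.* The order of paragraphs is not a stated order of work. Mapping comes before catheter preparation, the map is the basis for the target area, and needle extension is set against target tissue thickness before the catheter enters the ventricle. This suggests that a target may already be in mind. The documents are silent on timing.
- *That delivery as a whole can differ.* Count, volume and infusion time are specified identically, so the claim extends only to site selection.
- *That the bias can be expressed as excess procedural events.* The documents give no procedural risk by arm or by site pattern. Section 2.6.3 reports no major complications in a pooled series of 71 NOGA patients, although it notes CK-MB rises, and Section 9.1.3 reports no delivery complications in previous similar trials. Any assumed pair of event rates would be invented.

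**Conclusion.** The point holds as an unguarded opening for performance bias. An operator who must see an unmasked product also selects territory and sites, with discretion over segment spread and voltage, and nothing requires the selection to be fixed beforehand. Site selection could therefore differ by arm. The documents do not show that it does, or in which direction, and they do not allow the effect on safety or cMRI results to be sized.

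The conclusion assumes that the visible product reveals the arm, which is what Section 5.3 implies, and that no unpublished manual already requires a saved plan. The phase I, non-confirmatory aim lowers the stakes for the efficacy p-values. The primary safety comparison still relies on comparable delivery. This is a cheap improvement worth making, not a defect that invalidates the design.

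**What to change.** In Section 5.4, require that after electromechanical mapping the target area and intended sites are saved with a time stamp on the NOGA map before the operator sees the product. Record each departure from the saved plan with its reason, for example catheter stability. For the randomized cohort, tabulate by arm the segments injected, the unipolar voltage at injected sites, and planned versus delivered sites. Present these tables descriptively, since 15 per arm cannot support a reassuring test. The clinical site criteria stay as they are.

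In the same edit, reconcile Section 3.3 with Section 5.4 on ventricular coverage. Also reconcile the statement in Section 5.3 that investigators are blinded with the role of investigators as operators in Section 5.4.

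The cost is protocol wording, one worksheet line and a wait of a few minutes while the plan is saved. The record of planned sites is new, because the protocol provides only for tagging injected sites. No added staff or procedure is needed. Some sites will still move during the procedure for catheter stability, so the safeguard reduces the opening without removing it.
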